## Study Protocol

### Participants

20 participants were recruited for this study in a mixed factor study design. The recommended number of participants for repeated measures, between factors ANOVA is 36 (18 participants in each group). This was shown from a G-power calculation with a large effect size (0.4), a power of 0.8 and a significance level of 0.05. Due to time constraints, participant availability and feasibility, recruitment and data collection was completed after 20 participants. Participants were recruited via posters, social media, word of mouth and contacts made with multiple sclerosis (MS) therapy centres.

### Procedure

If interest was shown, an information sheet with inclusion and exclusion criteria was given to the participant and a link to a Novi Survey to gather information about their MS and health condition. Only the main researcher had access to this information on the Novi Survey. All participant information was pseudonymised according to their participant number. If the participant was eligible, they were randomly allocated to group A or group B by a random group generator on Microsoft ExcelTM, to organise suitable times for their sessions. Group A received a general massage for four sessions and group B received the mobilisation intervention for four sessions.

Participants were required to attend on four separate occasions, receiving the same treatment for each session. Though previous studies have recommended more sessions from their results, the time constraints on this project did not allow for more than four sessions per participant. Four sessions would still allow analysis for a cumulative effect, however previous research would indicate that eight - twelve sessions is more likely to show benefit from a manual therapeutic intervention. This was a single-blind trial, so participants were blind as to which treatment they were receiving. All testing took place at the Edinburgh Napier University Sighthill campus Engage building in a physiotherapy room which was maintained at standard room temperature (20-25°). The participants were asked to attend sessions at the same time on four consecutive weeks, to have a consistent gap between sessions.

Upon arrival, participants had the opportunity to read through the information sheet again and the researcher ran through the protocol with each participant. Participants were invited to ask any questions about the study before consent forms were given and encouraged to ask throughout the sessions if they wanted. They were informed they could withdraw from the study at any point and it would not affect their treatment. Their data could be removed up until the point of dissemination of summarised results. Once written consent was given, anthropometric measures were taken for age, weight, and height. Information was also taken regarding their most prominent symptoms and location of symptoms. Results from their Novi Survey were reviewed to go through their MS condition and Expanded Disability Status score.

The licensed massage therapist worked under their own liability and performed both treatments on all participants for this study. The therapist received training to perform the spinal mobilisation intervention. This training was monitored with force plate measurements (Kistler Instruments Ltd., Force Plate Type 2875A, Hampshire, UK) until the desired force was repeatedly applied. These forces were monitored during the intervention treatment sessions to retain the same treatment as much as possible.

For the spinal mobilisation intervention, the therapist performed a 30-minute spinal mobilisation intervention (rate = 0.37Hz, 22 beats per minute, force = less than grade 1, threshold of 80N, location = L1-L5). The force for both the intervention and the massage treatment were controlled using real-time force plate data collection. The massage therapy involved a 30-minute general massage, with no specificities or consistencies. Manual contact was applied on mid-lower back; rate and force magnitude of touch was not constant. This treatment acted as an alternative therapy, allowing comparison of the specificities of the intervention, and blinding of treatment.

During the first session, the participant carried out baseline tests for myometry, balance, pain, and fatigue pre their first session for both massage and intervention sessions. The myometer, balance and pain tests were then tested post the first session. During the subsequent three sessions, the participants completed the myometer, balance and pain tests post treatment and the final fatigue test following their last session. Participants therefore completed five sets of tests for the myometer, balance and pain, to test the cumulative effect. The fatigue test was only completed pre and post all treatment sessions due to the set-up of the questionnaire. Once all testing sessions were complete, participants were thanked for their

contribution and given a debrief sheet with further information and contact details to give to their GP or carer as appropriate.

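### The arm is drawn at booking, before written consent and baseline testing, with no concealment or tester blinding described; drawing it after baseline would lower a bias risk at almost no cost

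*Combined protocol and SAP*

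**What the plan says.** All of this is in the combined protocol and SAP.

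- **Draw.** Procedure: "If the participant was eligible, they were randomly allocated to group A or group B by a random group generator on Microsoft Excel". The reason given is "to organise suitable times for their sessions". At that point the person has received the information sheet and the survey link but has not attended.
- **Consent.** Procedure, describing the first visit: the researcher goes through the protocol and takes questions, and consent forms follow. Then: "Once written consent was given, anthropometric measures were taken for age, weight, and height".
- **Baseline.** Later in the same section, at session 1: "the participant carried out baseline tests for myometry, balance, pain, and fatigue pre their first session".
- **Blinding.** "This was a single-blind trial, so participants were blind as to which treatment they were receiving". Nothing is said about concealing the list, about who took the measurements, or about whether that person knew the arm.
- **Logistics.** One therapist "performed both treatments on all participants for this study". The two treatments have the same length: "the therapist performed a 30-minute spinal mobilisation intervention" and "The massage therapy involved a 30-minute general massage". Both arms attend weekly for four weeks, with all testing in one room.
- **Analysis.** The Statistical Analysis Plan fits a repeated measures ANOVA by group and time to each outcome. There are five values per participant (two for fatigue), and the pre-treatment value is one of them.

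**The concern.** The order is draw, consent, baseline. Random allocation protects a comparison best when nobody who enrols or measures a participant can know the arm beforehand. Here there is a gap in which the arm exists and could be known, and two things in that gap could depend on it.

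1. **Who goes on to consent.** Someone drawn but not consented leaves no data and cannot be analysed as allocated. No rule for such people is given.
2. **The baseline reading.** It is the only pre-treatment value, so an error in it passes in full into change from baseline. Under Outcome Measures, myometry depends on the operator: the site is found by palpation and marked, and readings above a coefficient-of-variation limit are discarded. The higher side at this measurement also fixes which side is treated.

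The stated scheduling reason does not appear to need the arm, since therapist, session length, room and visit pattern are common to both groups.

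**Working it through.** **1. The plan's own figure, and whether moving the draw changes it.** The Participants section gives N = 36 for f = 0.4, power 0.8 and alpha 0.05. The number of measurements m and the correlation rho used are not stated. For the between-group F test, lambda = f² × N × m / (1 + (m − 1) × rho), with df 1 and N − 2.

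- m = 3, rho = 0.5: lambda = 0.16 × 36 × 3 / 2 = 8.64, power 0.815.
- m = 5, rho = 0.6: lambda = 0.16 × 36 × 5 / 3.4 = 8.47, power 0.807.

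For both pairs, 36 is the smallest even N reaching 0.80, so the figure reproduces under these assumed inputs (m = 5 with rho = 0.5 would give 32). At N = 20 the same two pairs give power of 0.545 and 0.537. The time of the draw is not an input, so moving it leaves all these values unchanged.

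**2. Effect of a baseline-only shift on the planned ANOVA.** Assumptions, none given in the documents: n = 10 per arm, outcome SD 1, compound symmetry, rho from 0.5 to 0.8, no true effect, and a shift b of 0.2 or 0.3 SD in one arm at baseline only. The five time points are from the plan.

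*Group by time:* lambda = (n/2) × b² × (1 − 1/5) / (1 − rho) = 4b² / (1 − rho), with df 4 and 72.

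| b | rho | lambda | rejection rate |
|---|---|---|---|
| 0.2 | 0.5 | 0.16/0.5 = 0.32 | 6.5% |
| 0.2 | 0.8 | 0.16/0.2 = 0.80 | about 9.0% |
| 0.3 | 0.5 | 0.36/0.5 = 0.72 | 8.6% |
| 0.3 | 0.8 | 0.36/0.2 = 1.80 | 15.0% |

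*Group main effect:* the shift is diluted to b/5, so lambda = (n/2) × (b/5)² / ((1 + 4 × rho)/5), with df 1 and 18.

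- b = 0.2, rho = 0.5: 5 × 0.0016 / 0.6 = 0.013, rejection 5.1%.
- b = 0.3, rho = 0.5: 5 × 0.0036 / 0.6 = 0.030, rejection 5.3%.
- Higher rho gives slightly less.

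The risk therefore falls on the group-by-time test and grows with rho.

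**3. Loss between draw and consent (illustration only).** If k people drawn to one arm are lost, 10 remain, and the lost would have differed by delta, that arm's mean moves by k/(10 + k) × delta.

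- k = 1, delta = 0.5 SD: 1/11 × 0.5 = 0.05 SD.
- k = 2, delta = 1 SD: 2/12 × 1 = 0.17 SD.
- k = 3, delta = 1 SD: 3/13 × 1 = 0.23 SD.

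Against a difference of 0.8 SD (f = 0.4, two groups, one measurement), the range is 0.05/0.8 = 6% to 0.23/0.8 = 29%. The documents report no such losses, so k and delta are assumptions.

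**The case against.** The order of events is not in dispute. The case against concerns mechanism, size and remedy.

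- **Loss mechanism.** Participants are described as blind, so their own decision not to consent should not depend on arm. This stands: arm-related loss needs a researcher who knows the arm, or a booking effect tied to it, and neither is shown. The loss route is the weaker of the two.
- **Room for tester influence.** Pain and fatigue are self-reported, and the analysed force-plate variables are automatic software output. This largely stands and narrows the baseline route mainly to myometry. There, device output does not settle the matter, because an operator chooses the site.
- **Size.** A two-sample t-test at 10 per arm gives 7.1% and 9.7% for shifts of 0.2 and 0.3 SD. That is not the planned test, so those figures should not be used. The ANOVA figures above replace them, and the shift itself remains assumed.
- **Reach of the remedy.** A reader might infer that moving the draw removes the bias. It does not. Four of the five test sets follow treatment, when a tester may know the arm under either order. Withdrawal at any time and removal of data up to dissemination are also allowed.
- **Timing.** The text is in the past tense and data collection is complete, so the draw cannot be moved for these 20. This stands and splits the remedy in two.

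Whether the generator gives equal arms is a separate question and forms no part of this point.

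**Conclusion.** The point holds as a weakness in the order of procedures. The arm is fixed before consent and before the only pre-treatment reading, nothing stated conceals it or blinds the tester, and no stated feature of the two arms requires the early draw. Baseline exposure is greatest for myometry and for the group-by-time test. The false-positive rates of 6.5-9.0% and 8.6-15.0% are conditional on an assumed shift, an assumed equal split and an assumed correlation. They show what a modest shift would do, without estimating what happened.

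A reader might go further and conclude that baseline readings were biased or that participants were lost selectively. The documents do not support that. They do not say who made the draw, who tested, or whether that person knew the arm. They report no losses, and they do not say whether the 20 counts people drawn, consented or completed.

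**What to change.** **For a continuation or repeat.** Book the four weekly slots without the arm. At session 1, draw or reveal the allocation only when written consent and all baseline tests, including the choice of treated side, are complete and recorded. Use a list prepared in advance and concealed from the person taking consent and baseline readings. The cost is a change to the procedure text and a prepared list, with no extra visits or participants and no loss of power. The small downside is that the therapist learns the arm just before treatment. The documents do not discuss the logistics of a draw during the first visit, so this should be confirmed as workable. Blinding of post-treatment testing needs its own provision.

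**For the 20 already tested.** Leave the procedure as it was carried out and describe it openly: state the order of draw, consent and baseline; report numbers drawn, consented and analysed by arm; state whether the tester knew the arm at baseline and afterwards; and analyse participants as allocated. This costs a short paragraph and a flow table. The group-by-time results for myometry should be read with this limitation in view.

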#### Statistical Analysis Plan

Participant data were extracted and stored on password protected Microsoft Excel spreadsheets on university computers. Data was reduced using the mean value of the 5 trials for each variable in each testing session was calculated, resulting in 5 values for each variable (except fatigue) and each participant used for statistical analysis. The fatigue scores were a numerical value between 0-20 and only collected twice, pre and post all sessions, resulting in 2 values for each participant. Data collected from their Novi Survey and in their first session were collated and summarised into mean, range and dispersion values for their anthropometric and MS data. Analysis was carried out on SPSS (version 23) using mean values with standard error dispersion values. All dependent variables for muscle response, single stance balance, sit-to-stand stability, pain, and fatigue scores were analysed each in a between-subjects repeated measures ANOVA. This was to determine differences between the two treatment groups and between the different time points.

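### The Expanded Disability Status score is collected but is neither a stated stratification factor nor a model term; with 20 participants this costs precision and exposes the group main effect to chance imbalance

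*Combined protocol and SAP*

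**What the plan says.** All places are in the combined protocol and SAP.

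- **Participants.** "20 participants were recruited for this study in a mixed factor study design". The target was larger: "The recommended number of participants for repeated measures, between factors ANOVA is 36 (18 participants in each group"), from a "G-power calculation with a large effect size (0.4), a power of 0.8 and a significance level of 0.05". Recruitment and data collection are reported as finished at 20.
- **Procedure, before allocation.** Interested people received "a link to a Novi Survey to gather information about their MS and health condition". Those found eligible were then "randomly allocated to group A or group B by a random group generator" in Excel. No stratum, block or minimisation factor is mentioned.
- **Procedure, first session.** After consent, "Results from their Novi Survey were reviewed to go through their MS condition and Expanded Disability Status score".
- **Statistical Analysis Plan.** "Data collected from their Novi Survey and in their first session were collated and summarised into mean, range and dispersion values". That is the only use of the MS data. Each outcome goes into a repeated measures ANOVA with a between-subjects group factor. No covariate is named, and the stated purpose is to find differences between groups and between time points.

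**The concern.** Single leg sway, sit-to-stand performance and the impact of fatigue can all plausibly depend on how disabled a participant is. A randomised trial of 20 can easily leave two groups that are not closely alike on such a factor, and the plan handles this neither at allocation nor in the model.

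The group main effect averages every measurement, including the one taken before any treatment. A stable difference in disability therefore passes straight into it. The plan names differences between the groups as a target and does not name the group-by-time interaction, so a reader may take the main effect as the treatment result. At stake are the precision of that comparison and how far it can be trusted in the one allocation that occurred.

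**Working it through.** **Inputs from the documents.** N = 20; planned 36 (18 per group); f = 0.4; power 0.8; alpha 0.05; five measurements per outcome, two for fatigue.

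**Assumptions not in the documents.** A 10:10 split; disability roughly normal; correlation r between disability and outcome of 0.3 to 0.7; correlation rho between repeated measurements of 0.5; 0.5 SD as a material imbalance.

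**1. The plan's own figure.** For the between-groups test with m measurements, lambda = f² × N × m / (1 + (m − 1) × rho), on 1 and N − 2 degrees of freedom. The plan does not give m or rho.

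- m = 5, rho = 0.6, N = 36: 0.16 × 36 × 5 / 3.4 = 8.47, power 0.807.
- m = 3, rho = 0.5, N = 36: 0.16 × 36 × 3 / 2 = 8.64, power 0.815.

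So 36 is reproducible. With m = 5 and rho = 0.5 the answer would be 32.

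**2. Chance of imbalance.** The standardised difference in mean disability has SD √(1/10 + 1/10) = 0.447 at N = 20 and √(1/18 + 1/18) = 0.333 at N = 36.

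| Difference exceeds | N = 20, 10:10 | N = 20, unblocked draw | N = 36 |
|---|---|---|---|
| 0.5 SD | 26% | 28% | 13% |
| 0.75 SD | 9% | 10% | 2.4% |
| 1 SD | 2.5% | 3% | 0.3% |

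**3. Effect on the unadjusted group test when treatment does nothing** (simulation, five measurements, rho = 0.5). Over all allocations, the mean estimate is within 0.002 SD of zero and type I error is about 5%. When the imbalance exceeds 0.5 SD in one direction it averages 0.725 SD, so the estimated group difference shifts by about r × 0.725.

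| r | Shift (outcome SD) | False positives, imbalance > 0.5 SD | False positives, other allocations |
|---|---|---|---|
| 0.3 | 0.22 | 7.6–7.8% | 4.0% |
| 0.5 | 0.36 | 12.0–12.2% | 2.4% |
| 0.7 | 0.51 | 17.9–18.2% | 0.4% |

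The ranges in the third column are two separate runs. The last two columns average back to nominal: at r = 0.5, 0.264 × 12.2% + 0.736 × 2.4% = 5.0%. With rho = 0.7 and r = 0.7 the conditional figure is 16%.

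**4. Group-by-time.** The contrast in change from baseline shifts by less than 0.01 SD under the same imbalance, with false positives of about 5%, when disability affects level but not response.

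**5. With the covariate.** Conditional type I error returns to about 5% at all three correlations. The SD of the estimated group difference falls from 0.35 to 0.33 (r = 0.3) or 0.27 (r = 0.5).

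For power, let v = (1 + (m − 1) × rho) / m. This is 0.6 for m = 5. Unadjusted, lambda = 0.16 × 20 / 0.6 = 5.33 on 1 and 18 df, power 0.59. Adjusted, lambda = [0.16 × 20 / (v − r²)] × (1 − 1/17) on 1 and 17 df:

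- r = 0: 3.2 / 0.60 × 0.941 = 5.02, power 0.56.
- r = 0.3: 3.2 / 0.51 × 0.941 = 5.91, power 0.63.
- r = 0.5: 3.2 / 0.35 × 0.941 = 8.61, power 0.79.

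Fatigue has two measurements, so v = 0.75. Unadjusted lambda is 3.2 / 0.75 = 4.27, power 0.50; adjusted power is 0.47, 0.52 and 0.64 for r = 0, 0.3 and 0.5.

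**The case against.** Four arguments go the other way.

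**Randomisation already deals with this.** A reader might infer that the design is biased or that its error rate is inflated. The documents do not support that. Step 3 shows an unbiased estimate and about 5% error over all allocations, with rates below 5% when the groups happen to be alike. This stands. What remains is lost precision, and a shift that depends on the imbalance that actually occurred.

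**The size is easily overstated.** Suppose 8 of 20 participants are more disabled, they split 6 v 2, and the strata differ by 1 SD. A reader might treat this as a fixed shift of 0.4 SD against a standard error of 0.447 SD and read 13.5% false positives from a non-central t. Mixing strata also widens the within-group SD, and direct simulation gives about 10–11%. A split that uneven or worse has a probability of 17% under these inputs. The eligibility criteria are not in the documents, so the actual range of disability is unknown.

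**The timing and the draw are inferred.** A reader might infer that the score was in hand before allocation and that the draw was unrestricted. The survey on MS and health precedes allocation, but the score is named only at the first-session review, and a random group generator may well produce equal groups. This stands against a firm criticism of the allocation. It does not touch the analysis, because the score was available by the first session in any case.

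**The time factor gives protection.** Every outcome has a pre-treatment value, and a fixed level difference cancels in the interaction. This stands for the interaction. It does not protect the main effect, and the plan does not say which term answers the treatment question.

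**Conclusion.** The point holds as a matter of precision and of the realised comparison, not of bias. An available baseline score with a plausible bearing on balance and fatigue is used only descriptively, in a trial that stopped at 20 of a planned 36. A disability difference above 0.5 SD has about a 1 in 4 chance, twice that at the planned size; one above 1 SD is rare. If such an imbalance occurred, the unadjusted group main effect would give false positives at about 8% to 18%, depending on the assumed correlation.

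These figures rest on the assumed r, rho, normality and equal groups. The power figures also assume f = 0.4, and at rho = 0.6, which gives the planned 36 with five measurements, unadjusted power at 20 is 0.54 rather than 0.59. If the group-by-time term is taken as the treatment test and disability affects level only, the imbalance does not distort it. The documents give no evidence either way on whether response varies with disability.

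**What to change.** Enter the baseline Expanded Disability Status score as one covariate in the balance and fatigue analyses, and report the score by group. If results have already been seen, label the adjusted analysis post hoc and show it beside the unadjusted one. State which model term answers the treatment question, so that readers know whether the adjustment bears on it.

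No new data are needed. The cost is one of 18 error degrees of freedom and, if disability is unrelated to the outcome, a fall in power from about 0.59 to 0.56 (0.50 to 0.47 for fatigue). The gain at r = 0.3 to 0.5 is a rise to 0.63 to 0.79 (0.52 to 0.64 for fatigue).

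Stratified blocked allocation can no longer be applied, because recruitment is complete; its absence can be noted as a limitation.

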#### Outcome Measures

Participants self-reported pain using a visual analogue scale (VAS). The VAS uses a pain rating scale from 0-10, 0 represented no pain and 10 represented worst pain felt. Participants were given a visual scale to rate their resting lower back pain in each of the testing sessions.

Participants completed a shortened version of the Modified Fatigue Impact Scale consisting of five questions on the impact of fatigue in their lives over the past 4 weeks. There was a total possible score of 20. This was completed at the start of the first session and at the end of the fourth session.

Myometer tests were completed using a myometer palpation device (MyotonPRO, Myoton Ltd., London UK). This previously validated handheld device has been documented to give reliable results for muscle stiffness, tone and elasticity. The myometer is a form of indenter and the main form of measuring viscoelastic properties of tissue. The indenter is placed above the desired tissue and produces a series of short force impulses from the electromagnetically activated device. This causes small deformations in the tissue for a predetermined period, to which the tissue responds with damped oscillations determined by its viscoelastic properties. These oscillations are recorded by an accelerometer on the testing end of the indenter, recording the muscle deformation characteristics via an acceleration signal. Stiffness is calculated as the ratio of resisting force response and the change in length of the tissue, tone is calculated as responding tissue acceleration signal frequency and elasticity is calculated as the logarithm decrement of the acceleration signal dampening frequency (the natural log of the ratio of two successive the acceleration signal peaks). The stiffness, tone and elasticity parameters are reported as a mean of these impulses along with a coefficient of variation (CV). Values were only accepted if the CV was less than 3%, complying with the manufacturer recommendations.

Measurements were collected on both sides of erector spinae muscle and using the higher mean value to determine the stiffer side of the spine for treatment. Measurements were taken from the central belly of this muscle by asking the participant to lift their head and feet

at the same time, contracting their back muscles to allow for muscle belly palpation. This spot was then marked and measured.

The participants then performed two balance tests positioned on the force plates. Test one involved a single leg stance test, collecting measurements for body sway total path length, anterior-posterior path length, medial-lateral path length and velocity using the tracked centre of pressure recording. The second test used was a sit-to-stand test. This required a calibration of force plates to the participant's body weight. Participants were seated on a chair directly in front of the force plate, with their feet resting on the force plate. They were asked to move from a sit to stand position, using only their leg strength. This was repeated five times. The researcher was available to help at any time if participants felt uncomfortable or unstable during the tests or therapy session. Participants were encouraged to rest between the balance tests or at any time they felt tired.

The software used to collect the force data (Kistler, MARS) gave an automatic output for the variables used in analysis. These were centre of pressure body sway velocity, rising index (the percentage of body weight applied to the force plates during the standing movement) and weight transfer (the time taken to stand). A total of five testing sessions were completed for each participant, pre and post session one, and post sessions two, three and four.

